18.4 Missing Date of Investigational Product

When the date of the last dose of investigational product is missing for a subject in the Safety Set, all efforts should be made to obtain the date from the investigator. If it is still missing after all efforts, then the last visit date when investigational product was returned will be used in the calculation of treatment duration.

18.5 Missing Date Information for Prior or Concomitant Medications

For prior or concomitant medications, incomplete (i.e., partially missing) start dates and/or stop dates will be imputed. When the start date and the stop date are both incomplete for a subject, impute the start date first.

18.5.1 Incomplete Start Date

The following rules will be applied to impute the missing numerical fields. If the stop date is complete and the imputed start date is after the stop date, then the start date will be imputed using the stop date.

MISSING DAY, MONTH AND YEAR

- The entire date is missing, then the first dose date of investigation product will be assigned to the missing fields.

MISSING DAY AND MONTH

- If the year of the incomplete start date is the same as the year of the date of the first dose of investigational product, then the day and month of the date of the first dose of investigational product will be assigned to the missing fields.
- If the year of the incomplete start date is not the same as the year of the date of the first dose of investigational product, then set day to “01” and month to “01”.

MISSING MONTH ONLY

- The day will be treated as missing and both month and day will be replaced according to the above procedure.

MISSING DAY ONLY

- If the month and year of the incomplete start date are the same as the month and year of the date of the first dose of investigational product, then the day of the date of the first dose of investigational product will be assigned to the missing day.
- If the month and year of the incomplete start date are not the same as the month and year of the date of the first investigational product, then set day to “01”.

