4. SUBJECT POPULATION SETS

For all assessments, the treatment used will be the actual treatment and will be assigned according to the treatment period in which the assessment is performed.

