11.1 Adverse Events

Adverse events will be coded using the Medical Dictionary for Regulatory Activities (MedDRA), Version 17.0 adverse events dictionary.

An AE (classified by preferred term) that occurs during the study will be considered a TEAE if:

- it has a start date and time on or after the first dose of investigational product and up to 7 days after the last dose of study drug, or
- it has a start date and time before the date and time of the dose of investigational product (i.e. it is part of the patient's medical history), but increases in severity on or after the date and time of the dose of investigational product.

Adverse events will be collected from the start of first dose until 1 week post-treatment visit, which is at 7±2 days after receiving the last dose of investigational product. All SAEs with an onset within 30 days after the last dose of investigational product will be collected. In addition, any related SAEs with an onset >30 days after last dose of investigational product will also be collected.

Any pre-treatment adverse event starting between the first date of the observation period to the administration of investigational product in Period 1 will be considered as medical history. Any AE starting after first dose of investigational product will be captured for this study.

An overall summary of TEAEs will be provided by treatment, by exposure, by time of onset, including the number and percentage of subjects who experience, and absolute count of events by treatment for:

- Any TEAE
- Any serious TEAE
- Any TEAE related to investigational product in the opinion of the investigator

- Any TEAE leading to dose discontinuation from the study
- Any severe TEAE.
- Any TEAEs leading to Death
- The number and percentage of subjects reporting TEAEs will be tabulated in the following ways:
 - By SOC, preferred term and treatment (including absolute count of events)
 - By SOC, preferred term, and maximum severity
 - By SOC, preferred term, and serious TEAE
 - By SOC and preferred term for TEAEs related to investigational product in the opinion of the investigator

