18.6 Missing Date Information for Adverse Events

18.6.1 Incomplete Start Date

Follow same rules as in Section [18.5.1](#).

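### An adverse event with an incomplete start date that fits both crossover periods is always imputed to Period 1, so about half of such events go to the wrong dose

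*SAP*

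**What the plan says.** SAP 18.6.1, on incomplete adverse event start dates, has one line: "Follow same rules as in Section" 18.5.1. That section is the rule for prior and concomitant medications:

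- Whole date missing: "The entire date is missing, then the first dose date of investigation product will be assigned to the missing fields".
- Day and month missing, year equal to the first-dose year: "then the day and month of the date of the first dose of investigational product will be assigned to the missing fields". In any other year the start becomes 01 January.
- Day missing: the first-dose day if the month and year match the first dose. Otherwise, where they differ from the "month and year of the date of the first investigational product, then set day to" 01.
- Stop-date check: "If the stop date is complete and the imputed start date is after the stop date", the stop date replaces the imputed start.

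The first study dose is Visit 1a, in Period 1. No branch uses the first dose of Period 2, the visit of report, or the treatment at the time of report. SAP 11.1 does refer to the first dose in each treatment period when it defines baseline weight for the weight-adjusted dose, so the authors name the period-specific dose when they mean it.

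SAP 4 says that the treatment "will be assigned according to the treatment period in which the assessment is performed". SAP 11.1 says: "An overall summary of TEAEs will be provided by treatment, by exposure, by time of onset", and adds a summary by weight-adjusted dose group, built from the period-specific dose and weight (Table 4.2.5). SAP 2.1 specifies two 12-week periods with no washout.

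**The concern.** In a parallel-group trial an imputed start date mainly settles whether an event is treatment-emergent, and anchoring on the first dose is the cautious choice. In this crossover the imputed date can also decide whether the event counts under 500 U or 1000 U. Caution is not at issue here: under SAP 11.1 any onset from the first dose to 7 days after the last dose is already treatment-emergent, in whichever period it falls.

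Medications and adverse events also differ in a way that makes the borrowed rule unsafe. SAP 9 counts a medication under a treatment if it is recorded at least once in that treatment's period, so an early imputed start adds a period without removing one. No such provision exists for adverse events, so an early imputed start can take an event off the dose under which it occurred. Safety of the two dose levels is a secondary objective, and the tables by treatment and by weight-adjusted dose group would carry the error.

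**Working it through.** The plan states no figure on this point, so there is none to reproduce.

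**Inputs.** The rules of SAP 18.5.1; two periods of 84 days without washout (SAP 2.1); a treatment-emergent window to 7 days after the last dose (SAP 11.1); 12 subjects allocated to A/B or B/A with equal probability from site schedules (SAP 2.2). The share of adverse events with incomplete dates is not given; 2% to 20% is assumed for illustration.

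**One example, with an assumed first dose on 24 March.** Period 2 starts 84 days later, on 16 June. Take a true onset on 20 June, in Period 2.

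- Recorded as June only: imputed to 1 June, Period 1. Wrong dose.
- Recorded with the year only: imputed to 24 March, Period 1. Wrong dose.
- Nothing recorded: imputed to 24 March, Period 1. Wrong dose.

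An onset recorded as July is imputed to 1 July, Period 2, which is correct. Of the 30 days in June, 15 lie in each period, and all go to Period 1.

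**All start dates.** The rules were applied to every first-dose date in a non-leap year and every possible onset day. Period 1 is days 1 to 84, and the Period 2 window is 84 + 7 = 91 days. An onset is ambiguous if the known date parts allow days on both sides of the crossover. Stop dates were not used in this count.

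| Missing part | Ambiguous onsets imputed to Period 1 | Ambiguous onset days truly in Period 2 | Share of all Period 2 onset days relabelled, mean (range over start dates) |
|---|---|---|---|
| Whole date | 100% | 52.0% (91/175) | 100% |
| Day and month | 100% | 51.7% | 87% (0 to 100%) |
| Day only | 100% | 50.0% | 16% (0 to 33%) |

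No Period 1 onset is ever moved to Period 2. The stop-date check can only move a start earlier, so it cannot undo the error.

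**Effect on the dose contrast.** Let a share m of events have a wholly missing date, and let r500 and r1000 be the true event counts per child per period, with no period effect. The Period 1 dose gains m times the Period 2 count, and the Period 2 dose loses the same amount.

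For one A/B child and one B/A child (balanced sequences):

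- 500 U total = (2 − m)·r500 + m·r1000
- 1000 U total = (2 − m)·r1000 + m·r500
- Difference = 2(1 − m)(r500 − r1000), against a true 2(r500 − r1000)

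The contrast shrinks by the factor 1 − m, that is by 2% to 20% for m of 2% to 20%. No spurious difference arises when the rates are equal.

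For 8 A/B and 4 B/A children with equal rates:

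- 500 U = 8(1 + m) + 4(1 − m) = 12 + 4m
- 1000 U = 8(1 − m) + 4(1 + m) = 12 − 4m

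| m | 500 U : 1000 U count ratio, true value 1 |
|---|---|
| 2% | 12.08/11.92 = 1.013 |
| 5% | 12.2/11.8 = 1.034 |
| 10% | 12.4/11.6 = 1.069 |
| 20% | 12.8/11.2 = 1.143 |

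With 4 A/B and 8 B/A the ratio inverts. If the site schedules behave like simple randomization (an assumption, since no study-wide balance is stated), exactly 6:6 has probability 924/4096 = 23%, and 8:4 or more uneven has 1 − (792 + 924 + 792)/4096 = 39%.

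**Per event.** With 12 children under each dose, one relabelled event changes a subject-incidence row by at most 1/12 = 8.3 points under either dose.

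**The case against.** The strongest reply is that the premise is inferred. No SAP sentence says that an adverse event takes the dose of the period in which it began. SAP 4 speaks of the period in which an assessment is performed, which could mean the period of report, and SAP 9 handles medications by the period in which they are recorded. On that reading the imputed date would not choose the dose. This stands as a limit. Attribution by onset is nevertheless the natural reading of tables by treatment, and if attribution by report is meant, the SAP should say so.

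The trigger is also likely to be rare. Protocol 9.0 requires the investigator to report the onset date and whether onset fell during or within 24 hours after dosing. Dosing is twice weekly under professional supervision, attacks are entered daily in the eDiary (Protocol 6.9), and discrepancies are queried (Protocol 11.0). A wholly missing date, the worst case above, is the least plausible pattern. This also stands.

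Four stronger readings are tempting, and the documents do not support them:

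- That all incomplete dates go to Period 1. Day 01 of a month wholly inside Period 2, or 01 January once Period 2 has begun, is imputed correctly.
- That the rule produces a false period effect in the results. The SAP plans no adverse event table by period and no test on adverse events.
- That it favours one dose. Period 1 is 500 U in A/B and 1000 U in B/A, so with balanced sequences and equal missingness the effect is dilution.
- That every misplaced event moves an incidence by 8 points. The rows count subjects, so a row changes only if the child has no other qualifying event under the affected dose. Every attack after the first dose is recorded as an adverse event, so many children may already count under any TEAE for both doses. The ceiling matters mainly for rare preferred terms.

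**Conclusion.** The point holds. Followed as written, SAP 18.6.1 imputes every adverse event whose incomplete date fits both periods to Period 1, and about half of those onset days belong to Period 2. SAP 17 and the rest of SAP 18 contain no correction, and no sensitivity analysis of the imputation is planned.

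The wrong-dose consequence rests on attribution by onset date, inferred from SAP 4 and SAP 11.1. The size rests on an assumed share of undated events and on equal event rates in both periods: a dose contrast diluted by 2% to 20% with balanced sequences, and a count ratio of 1.013 to 1.143 at 8:4 when the true ratio is 1. The real effect is probably near or below the lower end. This should be fixed because the stated rule gives a wrong answer and the correction gives up nothing; it does not threaten the trial's conclusions.

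**What to change.** In SAP 18.6.1, replace the cross-reference to 18.5.1 with a period-aware rule:

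1. State that adverse events are attributed to the treatment of the period in which they begin.
2. Where the known date parts allow both periods, bound the onset by the visit or period at which the event was first reported and by any stop date. Impute to no earlier than the first dose of the period so identified.
3. Flag in Listing 7.1.1 any event whose period remains ambiguous, and add a sensitivity tabulation that assigns it to each dose in turn. This shows the range without counting one event under both doses in the same table.

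The medication rule in 18.5.1 can stay as it is. The cost is a few lines of SAP text and the matching programming. No new data are needed if the visit or date of first report is held in the study database; this should be confirmed.

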18.5.2 Incomplete Stop Date

The following rules will be applied to impute the missing numerical fields. If the imputed stop date is before the start date (imputed or non-imputed start date), then the imputed stop date will be equal to the start date.

MISSING DAY, MONTH AND YEAR

- If the entire date is missing, then the last dose date of investigation product will be assigned to the missing fields.

MISSING DAY AND MONTH

- If the year of the incomplete stop date is the same as the year of the date of the last dose of investigational product, then the day and month of the date of the last dose of investigational

product will be assigned to the missing fields.

- If the year of the incomplete end date is not the same as the year of the date of the last dose of investigational product, then set day to “31” and month to “12”.

MISSING MONTH ONLY

- The day will be treated as missing and both month and day will be replaced according to the above procedure.

MISSING DAY ONLY

- If the month and year of the incomplete stop date are the same as the month and year of the date of the last dose of investigational product, then the day of the date of the last dose of investigational product will be assigned to the missing day.
- If the month and year of the incomplete end date are not the same as the month and year of the date of the last investigational product, then set day to last day of the month of the incomplete end date.

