9. PRIOR AND CONCOMITANT MEDICATION

The version dated 01 Mar 2014 of the WHO Drug Dictionary will be used to classify prior and concomitant medications by preferred drug name.

Any therapy received during the 9 months prior to screening for the management of angioedema attacks should be recorded, including overall start and stop dates if known, and the HAE indication (i.e., long-term prevention, acute treatment, short-term prevention). For any medication used in the management of HAE that has a start date prior to Treatment Period 1 and is planned to be continued in the treatment periods of the study, a stop date prior to the first dose of study drug in Treatment Period 1 should be entered into the eCRF. Any subsequent use of this medication should be recorded as a concomitant medication with a new start date.

HAE therapy received 9 months prior to screening will be recorded. Otherwise all medications taken within 1 week prior to Day 1 of Treatment Period 1 will be recorded and entered into the eCRF.

Concomitant treatment refers to all treatment taken between the dates of the first dose of investigational product and the end of the follow-up period, inclusive.

Concomitant medications taken from the start of dosing through 1-week post-treatment will be recorded in the eCRF. For medications associated with management of angioedema attacks, study personnel will record the start/stop dates, dose, unit, frequency, route of administration, and indication (if known) in the subject's eCRF. For medications not associated with the management of HAE, study personnel will record the start/stop dates, route of administration, and indication for which the medication was administered in the subject's eCRF.

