Prior medication usage will be summarized by the number and percentage of subjects receiving each medication by treatment sequence within the Safety Set. Concomitant medication usage will be summarized by the number and percentage of subjects receiving each medication by treatment within the Safety Set. Medications can be counted both as prior and as concomitant medication. Multiple medication usage by a subject in the same preferred term category will be counted only once. Concomitant medications will also be summarized by the number and percentage of subjects receiving each medication by treatment within the Safety Set. For this summary, concomitant medications will be assigned to a treatment if they are recorded at least once within the period corresponding to that treatment.

All non-study medications taken during the study will be listed and prior, concomitant (taken from the start of dosing through 1-week post-treatment in the eCRF) and post medications (taken after the 2nd period) will be flagged.

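### SAP 18.5.2 can overwrite a partial stop date that lies before the trial with the first dose date, so a past HAE therapy counts as concomitant under the Period 1 dose

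*SAP*

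**What the plan says.** SAP 18.5 fixes the order of imputation: "When the start date and the stop date are both incomplete for a subject, impute the start date first".

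For the start (SAP 18.5.1), the rule for a wholly missing date is: "The entire date is missing, then the first dose date of investigation product will be assigned to the missing fields". If only the year is known and it is the year of the first dose, the text continues: "then the day and month of the date of the first dose of investigational product will be assigned to the missing fields". There is one safeguard. When the stop date is complete and the imputed start falls after it, "then the start date will be imputed using the stop date".

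For the stop (SAP 18.5.2), a date known to month and year goes to the end of that month, and a date known to the year goes to 31 December. The exception is a recorded part that matches the last dose, which sends the stop to the last dose date. A wholly missing stop has its own rule: "If the entire date is missing, then the last dose date of investigation product will be assigned to the missing fields". If the result is earlier than the start, whether that start was recorded or imputed, "then the imputed stop date will be equal to the start date".

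SAP 9 counts as concomitant any treatment from the first dose date onward, that date included. On dose groups it says "concomitant medications will be assigned to a treatment if they are recorded at least once within the period corresponding to that treatment". It asks for HAE therapy from the 9 months before screening, "including overall start and stop dates if known".

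**The concern.** An imputation rule should fill in what is unknown and leave what is known alone. Here the start can be pure invention (the first dose date) while the stop carries real information (a month or a year before the trial). The order check resolves the conflict in favour of the invented date.

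SAP 18.5.1 does the opposite for a complete stop date: it keeps the stop and pulls the start back. The protection is lost when the stop lacks only its day. Prior HAE therapy is a natural place for such records, because its dates are requested only if known and attack history may rest on recall (Protocol 6.1.1).

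At stake is the description of background therapy. Table 1.3.2 and the flags in Listing 4.3.1 could show a drug as used under one of the two doses when the record itself says it had already stopped.

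**Working it through.** The plan gives no figure to reproduce, so the check applies the SAP 18.5.1 and 18.5.2 rules literally to example records.

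**Inputs.** The dates are assumed for illustration. First dose: 15 Sep 2014. The last dose is 165 days later, 27 Feb 2015: two 12-week periods of 24 doses give 48 doses, hence 47 intervals averaging 3.5 days, and 47 × 3.5 = 164.5. Screening is 85 days before the first dose (1 day + 12 × 7 days).

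**Step 1: single records.**

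| Recorded start | Recorded stop | Imputed start | Stop before order check | Final stop | Concomitant? |
|---|---|---|---|---|---|
| missing | Mar 2014 | 15 Sep 2014 | 31 Mar 2014 | 15 Sep 2014 | yes |
| 2014 | Mar 2014 | 15 Sep 2014 | 31 Mar 2014 | 15 Sep 2014 | yes |
| missing | 2013 | 15 Sep 2014 | 31 Dec 2013 | 15 Sep 2014 | yes |
| Jan 2014 | Mar 2014 | 1 Jan 2014 | 31 Mar 2014 | 31 Mar 2014 | no |
| 2013 | Mar 2014 | 1 Jan 2013 | 31 Mar 2014 | 31 Mar 2014 | no |
| missing | 10 Mar 2014 | 10 Mar 2014 | complete | 10 Mar 2014 | no |

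In the first two rows the stop moves from the latest day its month allows, 31 March, to 15 September: 30 + 31 + 30 + 31 + 31 + 15 = 168 days. The final stop equals the first dose date, so the record meets the SAP 9 definition of concomitant and falls in Period 1. The last row is the first with the day of the stop known: the safeguard applies and nothing is moved.

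**Step 2: which patterns are affected.** The same rules were run on a grid of therapies that had truly ended 1 to 267 days before screening (every 7 days), lasting 3, 30 or 90 days, with the first dose on every third day of 2014. Share of records by final stop:

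- Complete stop, any start: 0% moved on study.
- Month-and-year stop, start complete or known to month and year: 0% moved.
- Month-and-year stop, start known to the year only: 29.8% moved to the first dose. These are the records whose start year is the first-dose year.
- Month-and-year stop, start missing: 100% moved to the first dose.
- Year-only stop, start missing: 60.1% moved to the first dose. In the other 6.9% + 33.0% = 39.9% the recorded year does not itself place the stop before the trial, and the stop goes to the last dose or to 31 December.

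The 29.8% and 60.1% depend on the assumed calendar. Which patterns are affected does not, and the 100% follows from the rule alone.

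**Step 3: size in the table.** With 12 children, one record changes one dose column of Table 1.3.2 by at most 1/12 = 8.3 percentage points. SAP 9 counts a child once per preferred term, so the change is zero if the child took the same drug in that period anyway.

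**The case against.** The best defence is that the pattern is narrow and its frequency unknown. Requesting dates if known does not show that many will be partial, and treating an unknown date as on treatment is a common, inclusive convention. Both points stand. They do not cover a stop whose recorded month or year lies before the first dose, because there the rule contradicts the record.

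Assignment to a dose could also be read as requiring an entry made during the period, without using imputed dates. But Protocol 6.3.2 collects start and stop dates and describes no entry per period, so dates are the likely route.

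A reader might infer more than the documents support:

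- *That a stop recorded as pre-trial can go to the last dose.* It cannot. That needs a wholly missing stop, or recorded parts that match the last dose, and such a record does not show that the therapy ended before the trial.
- *That Table 1.3.1 loses these therapies.* SAP 9 does not define prior medication by dates and lets a drug count as both prior and concomitant. SAP 7.2 also summarises prior HAE treatment as history.
- *That Table 1.3.2 would show prohibited C1 INH prophylaxis.* Drugs are classified by preferred name, no split by indication is described, and C1 INH for acute attacks is allowed (Protocol 6.10.2).
- *That rescue use by dose is distorted.* That comparison is a secondary endpoint (SAP 10.3), and Protocol 6.10.1 records for each attack whether treatment was given. Protocol 6.3.2 asks for start and stop dates of on-study attack medication without an if-known qualifier, so a missing stop there is hypothetical.

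**Conclusion.** The concern holds in a narrow form. When both dates are incomplete and the start is imputed to the first dose, a partial stop recorded before the first dose is overwritten with the first dose date. The past therapy then counts as concomitant under the Period 1 dose in Table 1.3.2 and Listing 4.3.1.

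This rests on a literal reading of SAP 18.5 and on dose assignment by overlap of dates with the period. The rate of occurrence cannot be derived from the documents. The efficacy endpoints do not use these dates, so the effect is confined to descriptive medication summaries and flags. It is a minor point, worth correcting because the written rule gives a wrong answer and the correction is easy.

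**What to change.** Amend SAP 18.5 as follows.

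1. State that no date is imputed outside its recorded year or month.
2. When the stop is partial and the imputed start falls after the latest date the stop allows, keep the stop within its recorded month or year and set the start no later than that stop. This extends to partial stops the protection SAP 18.5.1 already gives complete ones. In the first row of the table above, both dates would become 31 Mar 2014 and the record would not be concomitant.
3. For entries recorded as prior HAE therapy, cap the imputed stop at the day before the first dose. Protocol 6.3.1 supports this: an HAE drug that continues is closed before the first dose and re-entered as concomitant with a new start date.

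Check the same rule where SAP 18.6 reuses it for adverse events. Collection there begins with the first dose (SAP 11.1), so a pre-trial stop should be rare.

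The cost is a few lines of SAP text and derivation code, with no new data. The downside is small: a drug that truly continued but was not re-entered would be shown as prior only.
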